## **4.2 X-STOP® Interspinous Decompression (IPD®) System – Control Treatment**

The X-STOP® IPD® is an FDA-approved implant for the treatment of patients aged 50 years or older suffering from moderate symptoms of neurogenic intermittent claudication secondary to a confirmed diagnosis of LSS. The X-STOP® IPD® implant is a titanium metal implant designed to fit between the spinous processes in the lumbar spine. For additional information, please refer to the X-STOP® IPD® surgical technique supplied by the manufacturer with the device.

## **5 Study Overview**

### **5.1 Purpose**

The purpose of this study is to demonstrate that the success rate of the Study group receiving the Superior® Interspinous Spacer is not inferior to the success rate observed in the X-STOP® IPD® control group at 60 months follow-up, and that the Superior® Interspinous Spacer is safe when used in the treatment of moderately impaired LSS patients. This safety and effectiveness data will be used to satisfy the Agency-imposed Conditions of Approval of the Superior® Premarket Approval (PMA).

### **5.2 Study Endpoints**

#### **5.2.1 Composite Endpoint (Primary) – Individual Patient Success**

Subjects will be evaluated for success at each follow-up interval through 60 months. The primary study endpoint is the rate of overall subject success at the 60 month follow-up visit. An individual subject will be considered a success if they meet all of the following conditions at the 60 month follow-up:

Clinically significant improvement in outcomes compared to baseline, as determined by meeting the following:

- At least two of three domains of the Zurich Claudication Questionnaire (ZCQ)
  - Improvement in physical function by  $\geq 0.5$  points
  - Improvement in symptom severity by  $\geq 0.5$  points
  - “Satisfied” or “somewhat satisfied” as defined by a score of  $\leq 2.5$  points on the patient satisfaction domain
- No re-operations, revisions, removals or supplemental fixation at the index level(s)
- No major implant- or procedure-related complications:
  - No dislodgement, migration, or deformation
  - No new or persistent worsened neurological deficit at the index level
  - No spinous process fractures
  - No deep infection, death, or other permanent device attributed disability
- No clinically significant confounding treatments:
  - No epidural injections or nerve block procedures at index level, spinal cord

### 5.2.2 Secondary Endpoints

The secondary endpoints of this investigation are:

- To demonstrate the superiority of Superior® ISS to X-STOP® IPD® in effectively treating moderately impaired LSS patients as measured by 60 months postoperative overall success rates
- VertiFlex® Patient Satisfaction Survey – percent of patients scoring  $\leq 2.5$  on a 4 point scale
- Oswestry Disability Index (ODI) Version 2– compared to baseline, 15 point improvement (reduction in score) is considered clinically significant
- Visual Analogue Scale (VAS) - compared to baseline, an improvement in leg and/or back pain of 20 mm (on a 100 mm scale) is considered clinically significant
- To evaluate generic health status pre- and postoperatively using the SF-12 Short Form Health Survey, Version 2
- To evaluate maintenance of distraction defined by  $\leq 4$  mm of measurable decrease in the posterior disc space height on successive radiographs obtained at 6 weeks and 60 months postoperatively

### 5.2.3 Safety Endpoints and Role of CEC

Data will be evaluated for safety endpoints by an independent Clinical Events Committee (CEC). Safety outcomes will be determined by evaluating the type, frequency, severity, and relationship to device of adverse events through the 60-month time point for all subjects. Adverse events will be categorized as implant-related or procedure-related. All device-related events and major procedure-related failures reported by the site PIs will be adjudicated by the independent CEC. In addition, events reported as having unknown or undetermined relationship to the device by the site PI will be adjudicated by the CEC.

### 5.2.4 Other Endpoints

- Work status and time to return to work or normal activities of daily living (ADL)
- Narcotic use

### 5.3 Study Hypothesis

The primary hypothesis of this extended follow-up post approval study is that performance of the Superior® ISS remains clinically non-inferior to X-STOP® IPD® at 5 years post-surgery using the same non-inferiority margin as was used at 2-years. The hypotheses to be tested may be symbolically described as follows:

**Ho:**  $CCS_{\text{Superior}} - CCS_{\text{X-STOP}} \leq -0.10$  (inferior)

**Ha:**  $CCS_{\text{Superior}} - CCS_{\text{X-STOP}} > -0.10$  (not inferior)

At 2-years, follow-up compliance was 97% and 95%, and the observed overall success rates were 51.9% (95/183) and 49.7% (93/187) for Superior® ISS and X-STOP® IPD®, respectively. For the purpose of sample size analysis it was initially assumed: a) that at 5-years, follow-up compliance would be 85% in both groups (i.e., 155 Superior® and 161 X-STOP® IPD®); b) a device group difference equal to that observed at 2-years (i.e., 2.2%); and c) at 5-years 40% of Superior® ISS would achieve CCS (and so 37.8% is assumed for X-STOP® IPD®). In keeping with the original design, these hypotheses will be tested by determining the Bayesian posterior probability that  $(CCS_{\text{Superior}} - CCS_{\text{X-STOP}}) > -0.10$ . If the Bayesian posterior probability is at least equal to 0.95, then the hypothesis that Superior® ISS is non-inferior to X-STOP® IPD® at 5-years will be accepted. Non-informative beta(1,1) priors were assumed for both groups. With these assumptions, power is 73% and type 1 error is approximately 0.05. However, updated Month 36 results reflect a device group difference equal to 5.7%. Conservatively assuming a 5% difference, power increases to 87% and remains above 80% for device group differences larger than 3.5%.

The following superiority hypotheses will be tested if non-inferiority is demonstrated. By the closed testing principle there is no need for multiplicity adjustment.

**H0:  $CCS_{\text{Superior}} - CCS_{\text{X-STOP}} \leq 0$  (not superior)**

**Ha:  $CCS_{\text{Superior}} - CCS_{\text{X-STOP}} > 0$  (superior)**

The posterior probability that  $(CCS_{\text{Superior}} - CCS_{\text{X-STOP}}) > 0$  will be determined using Beta(1,1) priors for 5-year  $CCS_{\text{Superior}}$  and for 5-year  $CCS_{\text{X-STOP}}$ . If the posterior probability of superior is at least equal to 0.95, then a superiority claim will be made.

#### **5.4 Duration and Extent of Investigation**

Subjects included in the clinical investigation have returned for follow-up visits at 6 weeks ( $\pm 2$  weeks), 3 months ( $\pm 2$  weeks), 6 months ( $\pm 1$  month), 12 months ( $\pm 2$  months), 18 months ( $\pm 2$  months) and 24 months ( $\pm 2$  months) post-treatment to collect data for the primary evaluation of safety and effectiveness. Patients will continue to be followed annually ( $\pm 3$  months) until each patient has reached the 60 month time point. Study duration is anticipated to be extended by approximately 36 months to accommodate this additional follow-up.

### **6 Study Design**

This study is a prospective, multi-center, randomized controlled clinical trial comparing the Superior® ISS to the X-STOP® IPD® in the treatment of subjects aged 45 or older suffering from moderate symptoms of neurogenic intermittent claudication secondary to a confirmed diagnosis of moderate LSS at one or two contiguous levels from L1 to L5, i.e. from the L1-L2 level to the L4-L5 level. Implantation of the X-STOP® IPD® for patients aged 45-49 years is considered investigational. A maximum of 35 investigative sites in the U.S. enrolled subjects into the trial using a 1:1 randomization assignment and an adaptively selected sample size ranging from 250 to 350 subjects (125-175 enrolled into each group).

Up to an additional 50 patients (25 per group) were allowed to be enrolled to allow for loss to follow-up. In addition, prior to initiating the randomized trial, clinical sites were permitted to enroll 0-2 non-randomized “training” patients to receive the Superior® ISS. A total of 470 subjects were enrolled into the study. An investigative site is defined as a facility or facilities in the same general geographic location if they are under the control of a local Institutional Review Board (IRB). A total of 33 sites were authorized to enroll subjects. Two (2) failed to enroll any subjects and were discontinued from the trial. Of the remaining 31 sites that enrolled one or more subjects, six (6) have since discontinued participation, leaving 25 sites actively participating in the extended follow-up described by this protocol.

The numbers of patients in the final primary analysis set for effectiveness and safety included 190 patients randomized to Superior® and 201 patients randomized to the X-STOP® IPD® Control group. Eight (8) Superior® patients and 12 X-STOP® IPD patients are from 2 sites that are not participating in the PAS. This reduces the analysis set to 182 Superior® and 189 X-STOP® IPD®, respectively. Assuming 85% follow-up for the primary effectiveness endpoint at Month 60, there will be 155 Superior® patients and 161 X-STOP® IPD patients included in the primary non-inferiority evaluation.

After implantation of the Superior® ISS or the X-STOP® IPD® device, each Investigator provided a postoperative care regimen based on the subject’s specific need. The regimen may have included, but was not limited to: medications, a corset or brace, acupuncture, traction, physical therapy, chiropractic treatment, use of a TENS unit and massage therapy. The type and amount of the postoperative care were collected.

At each follow-up visit through 60 months, subjects will be interviewed to determine if they have experienced adverse events (AEs) since the previous follow-up visit. A neurological assessment will be performed for all patients at baseline and all follow-up visits. All subjects will be required to complete ZCQ, ODI, VAS, SF-12, and the VertiFlex® Patient Satisfaction questionnaires to evaluate disability, function, pain, quality of life and satisfaction at each follow-up visit. Subjects were also required to complete a VAS questionnaire to evaluate pain status at discharge.

The potential impact of spinal injections/nerve blocks use on the ZCQ was evaluated based on review of the medical literature. As these are potentially confounding of the ZCQ outcomes, epidural steroid injections or nerve block procedures at the treated level(s) will be deemed failures. Further, rhizotomy procedures at the treated level(s) will be deemed failures.

---

 Campbell's Operative Orthopedics (11th ed.) at 2281: "Although epidural steroid injections have been used in the treatment of spinal stenosis for many years, no scientifically validated long-term outcomes have been reported to substantiate their use, and most prospective reports show no statistically significant benefit. A meta-analysis showed that epidural steroids have little short-term advantage over placebo for treatment of leg pain." See also Carette S, Marcoux S, Truchon R, Grondin C, Gagnon J, Allard Y, Latulippe M. (1991) A controlled trial of corticosteroid injections into facet joints for chronic low back pain. *NEJM* 325(14):1002-1007. Jackson RP, Jacobs RR, Montesano PX (1988). Facet joint injection in low-back pain: A prospective statistical study. *Spine* 13(9):966-71.

With respect to spinal cord stimulators, because the use of a permanent implant would require a surgical procedure, this will be deemed a study failure.

Radiographic evaluations were performed at discharge, and at each scheduled follow-up visit and prior to any re-operations. The Investigator may obtain x-rays at unscheduled visits or to assess adverse events, if clinically indicated.

## **6.1 Study Population and Source of Subjects**

The study population consists of male and female subjects who are equal to or older than 45 years of age at time of enrollment, with moderate symptoms of neurogenic intermittent claudication and a confirmed diagnosis of moderate lumbar stenosis at one or two contiguous levels from L1 to L5, i.e level L1-L2 through level L4-L5, who met all inclusion/exclusion criteria and remain in follow-up from the original IDE study.

## **6.2 Randomization**

A computer-generated random list of treatment assignments (Master Randomization List) was created using a 1:1 ratio. Randomization occurred as close to the beginning of the treatment procedure as possible. Due to differences in the procedures, incision sizes, and operative positioning, subjects were not masked to their treatment arm after the surgery, but were not advised by site staff of their treatment assignment.

Sites used a web-based system to obtain treatment randomization assignment. The clinical sites were provided with system usage instructions, usernames, passwords, and technical support contact information. Randomization assignments were not re-used in the event that a subject withdrew from the study prior to surgery or became a study treatment failure.

## **6.3 Subject Eligibility Criteria**

The Principal or Sub-Investigator (PI or Sub-I) at each site was responsible for verifying that a potential study subject met all eligibility criteria and had none of the exclusion criteria. All patients who satisfied the inclusion and exclusion criteria and sign the Informed Consent were eligible to proceed to randomization and enrollment.

### **6.3.1 Inclusion Criteria**

*Candidates for this study met ALL of the following criteria:*

34. Male or female subjects  $\geq$  45 years of age.
35. Persistent leg/buttock/groin pain, with or without back pain, that is relieved by flexion activities (example: sitting or bending over a shopping cart)
36. Subjects who have been symptomatic and undergoing conservative care treatment for at least 6 months.
37. Diagnosis of degenerative spinal stenosis of the lumbar spine, defined as the narrowing of the midline sagittal spinal canal (central) and/or narrowing between the facet superior articulating process (SAP), the posterior vertebral margin (lateral recess), and the nerve root canal (foraminal).

38. Radiographic confirmation of at least moderate spinal stenosis which narrows the central, lateral, or foraminal spinal canal at one or two contiguous levels from L1-L5. Moderate spinal stenosis is defined as 25% to 50% reduction in lateral/central foramen compared to the adjacent levels, with radiographic confirmation of any one of the following:
  - Evidence of thecal sac and/or *cauda equina* compression
  - Evidence of nerve root impingement (displacement or compression) by either osseous or non-osseous elements
  - Evidence of hypertrophic facets with canal encroachment
39. Must present with moderately impaired Physical Function (PF) defined as a score of  $\geq 2.0$  of the Zurich Claudication Questionnaire (ZCQ)
40. Must be able to sit for 50 minutes without pain and to walk 50 feet or more
41. Subjects who are able to give voluntary, written informed consent to participate in this clinical investigation and from whom consent has been obtained
42. Subjects, who, in the opinion of the Clinical Investigator, are able to understand this clinical investigation, cooperate with the investigational procedures and are willing to return for all the required post-treatment follow-ups.

Note: In Criterion #5, all imaging used to confirm LSS need be completed within 3 months prior to enrollment. Radiographic confirmation of LSS may include MRI and/or CT. In the case of a transitional L5/L6 segment with a sufficiently prominent L6 spinous process, these could be included by requesting a deviation from the Sponsor.

### 6.3.2 Exclusion Criteria

*Candidates were excluded from the study if ANY of the following applied:*

8. Axial back pain only
  9. Fixed motor deficit
  10. Diagnosis of lumbar spinal stenosis which requires any direct neural decompression or surgical intervention other than those required to implant the control or investigational device
  11. Unremitting pain in any spinal position
  12. Significant peripheral neuropathy or acute denervation secondary to radiculopathy
  13. Lumbar spinal stenosis at more than two levels determined pre-operatively to require surgical intervention
  14. Significant instability of the lumbar spine as defined by  $\geq 3$ mm translation or  $\geq 5^\circ$  angulation
  8. Sustained pathologic fractures of the vertebrae or multiple fractures of the vertebrae and/or hips
  9. Spondylolisthesis or degenerative spondylolisthesis greater than grade 1.0 (on a scale of 1-4)
  43. Spondylolysis (pars fracture)
  44. Degenerative lumbar scoliosis with a Cobb angle of  $> 10^\circ$  at treatment level
  45. Osteopenia or osteoporosis. To confirm eligibility, at the Clinical Investigator's discretion, the following subjects may have a DEXA scan performed:
    - Women 65 or older
    - Postmenopausal women  $<$  age 65
    - Subjects with major risk factors for or diagnosed with osteoporosis or osteopenia
- If DEXA is required, exclusion is defined as DEXA bone density measurement T score  $\leq -2.5$
46. Morbid obesity, defined as Body Mass Index (BMI) greater than  $40\text{kg/m}^2$

47. Insulin-dependent diabetes mellitus
48. Significant peripheral vascular disease (diminished *dorsalis pedis* or tibial pulses)
49. Prior surgery of the lumbar spine
50. *Cauda equina* syndrome (defined as neural compression causing neurogenic bowel or bladder dysfunction)
51. Infection in the disc or spine, past or present
52. Evidence of active (systemic or local) infection at time of surgery
53. Active systemic disease such as AIDS, HIV, hepatitis, etc.
54. Paget's disease at involved segment or metastasis to the vertebra, osteomalacia, or other metabolic bone disease
55. Currently undergoing immunosuppressive therapy or long-term steroid use
56. Known allergy to titanium or titanium alloys
57. Tumor in the spine or a malignant tumor except for basal cell carcinoma
58. Known or suspected history of alcohol and/or drug abuse
59. Prisoner or transient
60. Life expectancy less than two years
61. Angina, active rheumatoid arthritis, or any other systemic disease that would affect the subject's welfare or outcome of the clinical investigation
62. Any significant psychological disturbance past or present, psychotic or neurotic that could impair the consent process or ability to complete subject self-report questionnaires
63. Involved in pending litigation of the spine or worker's compensation related to the back
64. Enrolled in the treatment phase of another drug or device clinical investigation (currently or within past 30 days)
65. Congenital defect of the spine
66. Pregnant or lactating

#### **6.4 Study Enrollment**

Each site evaluated consecutive spine patients for potential eligibility for study participation based on their age and medical symptoms. Patients could be prescreened and preliminarily excluded because of failure to meet basic inclusion or exclusion criteria. The Investigator could have approached patients who were considered suitable for entry into this study.

Patients were only considered evaluable after informed consent was obtained, eligibility for study entry had been verified by the Principal Investigator (PI) or designee at each site, randomization assignment had been provided, and treatment anesthesia administration had begun. Patients that were randomized, and had an anesthesia start time recorded, but were not treated with the control device or the investigational device due to unforeseen circumstances were considered in the Intent to Treat protocol analysis as a failure in his or her randomized treatment group. Patients that were randomized, but did not have a treatment administered, or an anesthesia start time recorded, were exited from the trial, and the reason for their screen failure was recorded and tallied.

## 6.5 Study Procedures

### 6.5.1 Screening

All potential subjects were screened for eligibility and were listed on the Screening/Enrollment Log. The Screening/Enrollment Log documented the date of screening, the results of screening, and the primary reason for excluding the subject (e.g. subject does not satisfy enrollment exclusion criteria or subject declined).

Eligible patients who agreed to participate in the study were required to sign an Informed Consent prior to undergoing any study-related screening procedures that were not standard of care. If the patient did not meet all eligibility criteria after signing Informed Consent and undergoing additional evaluation, the patient was considered a "screen failure" and was not be entered into the study. The reason for all screen failures was tabulated.

### 6.5.2 Baseline Assessment

The following baseline assessments were performed:

Subject Self-Report Questionnaires will be administered: 

• Zurich Claudication Questionnaire (ZCQ)

• Visual Analogue Scale (VAS)

• SF-12 version 2 Health Related Quality of Life

• Oswestry Disability Index (ODI)

Demographic/History and Physical Assessment: 

• Date of birth, race, ethnicity

• Gender, weight, height, and body mass index (BMI)

• Work status

• Nicotine use

• Leg and back pain

• Medical treatment

• Previous surgeries, co-existing diseases, any disabilities and concomitant medication

Neurological Assessment: 

• Muscle strength

• Sensory and Reflexes

• Range of motion

• Palpation of pulses

• Straight leg raise

• Femoral Stretch

Radiographic studies performed within 3 months of baseline: 

• Standing Anterior/Posterior Lumbar Spine view

• Lateral Lumbar Spine view

• Flexion/Extension Lateral Lumbar Spine views

• MRI or CT Scan

• DEXA Scan (If indicated)

### 6.5.3 Randomization and Enrollment

Randomization assignment was conducted at the end of the baseline period. After a patient had signed Informed Consent, and demonstrated eligibility based upon ALL inclusion/exclusion criteria, the patient was randomly assigned to a treatment group and surgery was scheduled. The randomization occurred as close as possible to the date of the treatment procedure.

Patients were only considered evaluable after Informed Consent had been obtained, eligibility for study entry had been verified by the Principal Investigator (PI) or designee at each site, randomization assignment had been provided, and treatment anesthesia administration had begun. Patients that were randomized, and had an anesthesia start time recorded, but were not treated with the control device or the investigational device due to unforeseen circumstances were considered in the Intent to Treat protocol analysis as a failure in his or her randomized treatment group. Patients that were randomized, but did not have an anesthesia start time recorded, were exited from the trial and the reason for their screen failure was recorded and tallied.

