
Number of Sites:
	
Only sites participating in the original IDE study will participate in this continued follow-up protocol. 25 IDE sites remain eligible for participation.

Study Enrollment:
	
Enrollment was completed in December 2011, with 391 randomized and treated patients and 28 non-randomized Superior® training patients.

Study Duration:
	
Subjects included in the original clinical investigation (G070118) returned for follow-up visits at 6 weeks, and 3, 6, 12, 18 and 24 months post-treatment to collect data for the primary evaluation of safety and effectiveness. Patients will be followed annually until each patient has reached the 60 month time point. Study duration is approximately 36 months as all patients have reached 24 months prior to the start of this continued follow-up protocol. Patients may potentially be followed annually for up to 10 years as part of a possible post-approval study.

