### 10.3 Randomization

1:1 for treatment to control. A randomized block design at each site was used.

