## 10.7 Missing Data and Loss-to-Follow-Up

In order to best preserve an intent-to-treat philosophy, the primary analysis will be done on the mITT group. Those subjects who withdraw, or who are lost (LTFU) after randomization, will be included in the analysis using Bayesian imputation. This analysis will be the primary analysis, but recognizing that there is no way, statistically, to handle these subjects without possibly introducing bias, a tipping point analysis will be conducted.

The tipping point sensitivity analysis will be conducted in which missing values in each group are separately assumed to be either successes or failures. Treatment group differences will be computed based on all possible combinations of assigning success or failure to the primary overall success endpoint to the patients in the two groups. For example, one scenario will be that all missing Superior device observations are failures and all missing X-STOP observations are successes. The next scenario would have one success and the remaining missing values as failure for Superior and all missing X-STOP as successes. For each scenario, the Bayesian posterior probability of non-inferiority will be determined. These results will be plotted using a dot plot with the number of missings assumed as failures for Superior on the x-axis and the number of missing assumed as failures for controls on the Y-axis. The dots will be color coded to indicate whether or not the primary statistical conclusion changes under each individual scenario. If the fraction of scenarios in which the statistical conclusion changes is small, the primary results will have been shown to be robust against assumptions concerning missingness.

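### Eligible patients who were randomized but exited before anesthesia are called screen failures and fall outside every planned analysis, so exits related to the assigned device would go untested

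*Combined protocol and SAP*

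**What the plan says.** **Timing.** Section 6.5.3 places assignment at the end of the baseline period: "the patient was randomly assigned to a treatment group and surgery was scheduled". It then adds that "The randomization occurred as close as possible to the date of the treatment procedure". Section 6.2 says "Randomization occurred as close to the beginning of the treatment procedure as possible". It also foresees withdrawal before surgery, since it says an assignment was not re-used in that case.

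**Who knew the arm.** Under section 6.2 the sites obtained the assignment through a web system, and no masking of sites or surgeons is described. Subjects were not told their assignment by site staff. The lack of subject masking is placed after surgery.

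**Exits before anesthesia.** Section 6.5.3 has this rule: "Patients that were randomized, but did not have an anesthesia start time recorded, were exited from the trial and the reason for their screen failure" (noted and counted). Section 6.4 has a similar rule. Section 6.5.1 uses the term screen failure for a patient found not to meet the eligibility criteria.

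**Analysis sets.** Section 10.4 defines mITT as randomized with an anesthesia start time, and uses it for the primary and all safety analyses. The per-protocol set needs 60-month data or an earlier failure. Section 10.7 says the primary analysis is on the mITT group, then that "Those subjects who withdraw, or who are lost (LTFU) after randomization, will be included in the analysis using Bayesian imputation". The tipping-point analysis follows from that set.

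**The concern.** An analysis set that begins at anesthesia preserves the randomized comparison if exits between assignment and anesthesia do not depend on the arm. Here the site held the assignment, surgery was scheduled after it, and the procedures differ visibly: section 12 gives a 15 mm incision for Superion and 40 mm for X-STOP. A site or surgeon could cancel or postpone differently by arm.

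If that happened, the primary, per-protocol and tipping-point analyses would all start after the selection. The plan asks for no table by arm, so a reader could not tell whether the exits were few and balanced or not. The label makes this worse, because it files eligible, randomized patients with those who never qualified.

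**Working it through.** **1. Can any planned analysis reach these patients?**

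| Analysis | Entry condition | Includes randomized patients with no anesthesia start? |
|---|---|---|
| Primary (mITT), 10.4 | randomized and anesthesia start recorded | No |
| Safety, 10.4 | mITT | No |
| Per-protocol, 10.4 | 60-month data without major deviation, or earlier failure | No: they were exited, with neither |
| Imputation and tipping point, 10.7 | mITT group | No |

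Patients anesthetized but not given a device are different: sections 6.4 and 6.5.3 count them as failures in their randomized arm.

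**2. Reproduce the plan's power.** Inputs from section 10.5: 155 and 161 patients, success 40% and 37.8%, margin -0.10, Beta(1,1) priors, cutoff 0.95. Summing both binomials exactly over all outcomes with P(difference > -0.10) at least 0.95 gives 74.3%. The normal approximation, Φ[(0.022 + 0.10)/√(0.40×0.60/155 + 0.378×0.622/161) − 1.645], gives 71.9%. The plan states 73%, so the rule is understood correctly. The exact false non-inferiority rate at 27.8% against 37.8% is 0.055.

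**3. How many exits would matter? (assumed)** Expected data: 0.40×155 = 62 and 0.378×161 = 60.9, taken as 61. With x successes in n patients, each posterior is Beta(x+1, n−x+1). I add k exits to the observed data, before any imputation.

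| Scenario | k | Data | Posterior of non-inferiority |
|---|---|---|---|
| None added | 0 | 62/155 vs 61/161 | 0.987 |
| Superion exits, all failures | 5 | 62/160 vs 61/161 | 0.978 |
| | 10 | 62/165 vs 61/161 | 0.966 |
| | 14 | 62/169 vs 61/161 | 0.952 |
| | 15 | 62/170 vs 61/161 | **0.948** |
| k Superion failures and k control successes | 5 | 62/160 vs 66/166 | 0.954 |
| | 6 | 62/161 vs 67/167 | **0.942** |

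**4. Effect on the error rate (assumed).** Let the true difference among all randomized be -0.10 (27.8% vs 37.8%), and let a share e of the Superion arm, all failures, exit while no control patient does. The analysed Superion rate is 0.278/(1−e).

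| e | Analysed rate | False non-inferiority rate |
|---|---|---|
| 0 | 27.8% | 0.055 |
| 2% | 28.4% | 0.069 |
| 5% | 29.3% | 0.094 |
| 10% | 30.9% | 0.157 |

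**5. Do the documents' counts reveal the number?** Section 6 states "A total of 470 subjects were enrolled into the study". The Protocol Summary gives "391 randomized and treated patients" plus 28 training cases, and 470 − 391 − 28 = 51. But 470 is also the enrolment ceiling: 350 + 50 + 70 = 470.

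The mITT arms are 190 and 201. Under simple 1:1 allocation the two-sided p is 0.61. Section 10.3 says "A randomized block design at each site was used", with no block size. Assuming 31 sites, each stopped at a random place in its last block of size B, SD = √(31 × mean over m = 0…B−1 of m(B−m)/(B−1)). This is 3.9, 5.1, 6.0 and 6.8 for B = 2, 4, 6 and 8. A gap of 11 or more then has normal-approximation probability 0.005, 0.03, 0.07 and 0.11 (simulation: 0.01, 0.04, 0.08 and 0.12). That is a weak hint at most.

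**The case against.** - **Patients did not know their arm.** A reader might infer that patients left because they disliked the assigned device. Section 6.2 says staff did not tell them, so the documents support only decisions by sites or surgeons. This stands.
- **The window was short.** Sections 6.2 and 6.5.3 both say randomization was kept close to the procedure. That limits the exposure. It does not settle how surgery came to be scheduled after assignment.
- **Section 10.7 does not clearly contradict 10.4.** Its opening sentence limits the analysis to mITT, so withdrawal after randomization can be read as withdrawal within that set. The wording is loose rather than in open conflict.
- **The counts prove nothing.** A reader might infer 51 hidden exits, or selective loss of Superion patients from 190 against 201. The 470 equals the ceiling. Even if it is real, the gap could be patients who failed screening after consent, before randomization. The smaller arm is also Superion, which does not fit avoidance of the larger control incision. This stands.
- **Moderate one-arm exits do not overturn the plan.** Adding 11 Superion failures gives 62/166 against 61/161, posterior 0.963, still above 0.95. This stands.
- **Other missing data will be larger.** At 85% follow-up the mITT set already has 182 − 155 = 27 and 189 − 161 = 28 missing. True, but the planned grid shows those and cannot show the exits.
- **These patients have no device and no planned 60-month outcome.** An all-randomized analysis would be assumption alone for them, and their absence from device safety summaries is reasonable. This argues for a sensitivity analysis, not for a new primary set.

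**Conclusion.** The gap is real and modest. Eligible, randomized patients without an anesthesia start are mislabelled and lie outside the mITT, per-protocol and safety sets and the tipping-point grid. No planned analysis would therefore test whether exits before anesthesia depended on the arm.

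The documents do not show that such exits occurred in any number, that they were unequal, or which device they would favour. Nor do they support a stated loss of power. The thresholds of 15 one-arm failures, or 6 opposed exits per arm, assume the planned success rates, 155 and 161 observed patients, and extreme outcomes for those who left. They show the scale at which the question matters, not an estimate of bias. If exits were few and balanced, a short table would settle most of the matter. This is a cheap improvement, not a flaw that invalidates the comparison.

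**What to change.** 1. Report, by arm and with reasons, every patient randomized but exited before anesthesia. Give the total for all sites and separately for the sites in the continued follow-up.
2. Stop calling them screen failures. Use a term such as randomized, not anesthetized.
3. Keep mITT as primary. Add one sensitivity analysis of all randomized patients at participating sites, extending the section 10.7 tipping-point grid to count these exits as missing in their assigned arm.
4. State in section 10.7 that, for the primary analysis, withdrawal after randomization means withdrawal within mITT.
5. Reconcile the timing wording in sections 6.2 and 6.5.3, and say who knew the assignment before anesthesia.
6. Reconcile the 470 enrolled with 391 + 28, or state that 470 was the ceiling.

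Cost: a few sentences, one table and one additional grid. The protocol says the exits and reasons were already logged, so no new data collection should be needed. The downside is more missing outcomes and a slightly less favourable robustness picture in that sensitivity analysis.
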